a. Routine tests include CBC with differential, reticulocyte count, Acute Care (sodium, potassium, chloride, CO2, glucose, BUN, creatinine), Mineral (serum calcium, phosphate, magnesium and albumin) and Hepatic (alkaline phosphatase, ALT, AST, total and direct bilirubin) Panels, uric acid, eGFR determination, and LDH. NOTE: PT and PTT will only be performed at baseline.

- b. Viral studies include Hep B surface antigen and Hep C antibody. If Hep C antibody positive, Hep C RNA PCR will be performed
- c. Pregnancy tests (urine or serum) for females of childbearing potential. A female of childbearing potential (FCBP) is a sexually mature female who: 1) has not undergone a hysterectomy or bilateral oophorectomy; or 2) has not been naturally postmenopausal for at least 24 consecutive months (i.e., has had menses at any time in the preceding 24 consecutive months). During extension phase, FCBP patients will have pregnancy tests per footnote "e". Local treating physicians will be required to submit results to NIH Clinical Center for review.
- d. Pregnancy tests (urine or serum) must occur within 10 14 days and again within 24 hours prior to prescribing lenalidomide for Cycle 1 (prescriptions must be filled within 7 days).
- e. FCBP with regular or no menstruation must have a pregnancy test (serum or urine) weekly for the first 28 days and then every 28 days while on therapy (including breaks in therapy); at discontinuation of lenalidomide and at Day 28 post the last dose of lenalidomide. Females with irregular menstruation must have a pregnancy test (serum or urine) weekly for the first 28 days and then every 14 days while on therapy (including breaks in therapy), at discontinuation of lenalidomide and at Day 14 and Day 28 post the last dose of lenalidomide (see **APPENDIX B**).
- f. Myeloma tests include serum protein electrophoresis, serum immunofixation, urine electrophoresis, urine immunofixation, serum free light chains, quantitative immunoglobulins, beta-2 microglobulin and will be performed at baseline and Day 1 of each cycle. Subsequent serum immunofixation, urine immunofixation, and urine electrophoresis will only be performed on those patients clinically indicated.

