- 1. Urine for protein electrophoresis (UPEP) and immunofixation to assess for monoclonal protein in the urine (Bence-Jones proteinuria) at screening, day 1 of each cycle during cycles 1-8, day 1 of (or within 7 days prior to day 1) every third cycle during cycles 9-32, and at treatment termination. In patients whose measurable disease is best determined by measuring Bence- Jones protein quantification, a 24 hour UPEP will be performed at baseline, day 1 of each cycle 1-8, and day 1 (or within 7 days prior to day 1) of every third cycle during extension phase I and II. Otherwise, 24-hr UPEP Bence-Jones quantification will be estimated from random UPEP specimens performed at baseline, day 1 of each cycle 1-8, and day 1 (or within 7 days prior to day 1) of every third cycle during extension phase [46].
- m. FDG-PET scan will be performed on patients at baseline, during cycles 1-8 if patient achieves CR and/or at the end of cycle 8 if no CR is achieved, during cycles 9-20 (extended dosing phase I) if patient achieves CR and/or at the end of cycle 20 if no CR is achieved, and during cycles 21-32 (extended dosing phase II) if CR is achieved or at treatment termination. FDG-PET scan can be performed +/- 21 days of intended cycle day. For patients who are on extended dosing with lenalidomide and are found to be negative by immunohistochemistry and flow cytometry of the bone marrow (MRD negative), clearance of abnormal protein in blood and/or urine does not mandate a repeated bone marrow and the results will be interpreted as complete response. However, a bone marrow will be repeated at the discretion of investigator. Diffusion weighted MRI (DW-MRI) will also be performed at the discretion of the PI. DW-MRI will be performed by standard techniques in the NCI Molecular Imaging Program. In follow up, PET/CTs and DW-MRIs will be done approximately annually, if feasible (i.e., missed scans will not be considered protocol deviations). Note: DW-MRIs are optional after Cycle 8.
- n. Bone marrow biopsy and aspirate will be performed on patients at baseline, during cycles 1-8 if patient achieves CR or at the end of cycle 8 if no CR is achieved, during cycles 9-20 (extended dosing phase I) if patient achieves CR or at the end of cycle 20 if no CR is achieved, and during cycles 21-32 (extended dosing phase II) if CR is not achieved or at treatment termination. Bone marrow aspirate and biopsy can be performed +/- 21 days of intended cycle day.

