## 6.3.1 Disease Parameters

- Measurable is defined as any of the following: serum M-protein is ≥ 1 g/dL or "measurable" urine M-spike is ≥ 200 mg/24 hours or serum kappa or lambda FREE light chain of 10 mg/dL along with an abnormal kappa to lambda free light chain ratio.
- The serum free light chain (FLC) assay is of particular use in monitoring response to therapy in patients who have oligo-secretory disease. When using this assay, it is important to note that the FLC levels vary considerably with changes in renal function and do not solely represent monoclonal elevations. Thus, both the level of the involved and the uninvolved FLC isotype (i.e., the involved/uninvolved ratio or involved-uninvolved difference) should be considered in assessing response. The serum FLC assay should be used in assessing response only if the baseline serum and/or urine M proteins are not "measurable" by traditional criteria (serum M protein ≥ 1gm/dL and/or urine M protein ≥ 200 mg/24), and the baseline level of the involved FLC is ≥ 10mg/dL and clonal (abnormal ratio). Patients included on the study on the basis of FLC alone (i.e., no measurable serum/urine) should be the only ones who are evaluated using FLC response criteria. The others should follow usual criteria and ignore FLC results.
- In order to be classified as a hematologic response, confirmation of serum monoclonal protein, serum immunoglobulin free light chain (when primary determinant of response) and urine monoclonal protein (when primary determinant of response) results must be made by verification on two consecutive determinations.
- Caution must be exercised to avoid rating progression or relapse on the basis of variation of radiological technique alone. Compression fracture does not exclude continued

Version Date: 01/01/2024

response and may not indicate progression. When progression is based on skeletal disease alone, it should be discussed with the PI before removing the patient from the study.

- Appearance of monoclonal or oligoclonal bands that are different from original isotype may not be defined as "relapse from CR". Oftentimes, such bands may indicate fluctuations in immunological parameters that are not reflective of MM disease. In these situations, immunofixation and electrophoresis will be interpreted by the clinician before being labeled as "relapse" [47, 48].

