- Random urine specimens will be performed day 1 of each cycle (cycles 1-8) and day 1 (or within 7 days prior to day 1) of every third cycle (cycles 9-32). 24-hr UPEPs will be performed to confirm and document "CR" response (once serum and random have become negative for monoclonal protein and immunofixation). In patients whose measurable disease is best determined by measuring Bence Jones protein quantification, a 24 hr UPEP will be performed at baseline, day 1 of each cycle 1-8, and day 1 (or within 7 days prior to day 1) of every third cycle during extension phase I and II. Otherwise, 24-hr UPEP Bence-Jones quantification will be estimated from random UPEP specimens performed at baseline, day 1 of each cycle 1-8, and day 1 (or within 7 days prior to day 1) of every third cycle during extension phase[46].
- As of amendment L (version date 05/17/2018), primary endpoint will be MRD (-) CR rate, therefore per the discretion of the investigator, patients without measurable disease may also be enrolled.
- 6.3.2 Response Criteria adapted from International Myeloma Working Group Criteria for Multiple Myeloma[49] and addition of nCR category[21, 50]
- 6.3.2.1 Evaluation of Response Criteria

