# • MRD(-) CR

Complete Response as defined below plus:

Absence of phenotypically aberrant clonal plasma cells by flow cytometry on bone marrow aspirates using the eight-color two-tube approach developed and validated by LP Flow cytometry lab for MRD detection in multiple myeloma with a minimum sensitivity of 1 in 10^5 nucleated cells or higher.

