# • Complete Response (CR)

Negative immunofixation on the serum and urine and disappearance of any soft tissue plasmacytomas and  $\leq$ 5% plasma cells in bone marrow

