# • Near Complete Response (nCR)

Defined as absence of myeloma protein on electrophoresis, independent of immunofixation status[50]

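### Study Calendar footnote m is looser than Section 6.3.2 on the protein evidence for complete response, and no text says which rule scores MRD(-) CR

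*Combined protocol and SAP*

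**What the plan says.** All references are to the combined protocol and SAP.

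- **Endpoint.** Section 6.3.2.1 defines MRD(-) CR as "Complete Response as defined below plus" a marrow negative by flow at a sensitivity of at least 1 in 10^5. CR there means "Negative immunofixation on the serum and urine and disappearance of any soft tissue plasmacytomas", together with no more than 5% plasma cells in the marrow.
- **Confirmation.** Section 6.3.1 says that the protein results behind a hematologic response "must be made by verification on two consecutive determinations". It adds that "24-hr UPEPs will be performed to confirm and document" CR once serum and random urine are negative.
- **Neighbouring categories.** nCR is "Defined as absence of myeloma protein on electrophoresis, independent of immunofixation status". Protein seen on immunofixation but not on electrophoresis is VGPR.
- **Footnote m (Section 3.4).** It covers patients on extended lenalidomide who "are found to be negative by immunohistochemistry and flow cytometry of the bone marrow (MRD negative"). For them, "clearance of abnormal protein in blood and/or urine does not mandate a repeated bone marrow and the results will be interpreted as complete response".
- **Testing after baseline.** Footnote f of the same calendar says: "Subsequent serum immunofixation, urine immunofixation, and urine electrophoresis will only be performed on those patients clinically indicated". Section 3.3.7.3 says the same for serum immunofixation. Footnote l and Section 3.3.7.4, however, schedule urine electrophoresis and immunofixation every third cycle in extension.
- **Marrow in extension.** Section 5.1.1 makes it optional for patients who are MRD negative at the end of cycle 8, whatever their response.
- **Primary analysis.** Section 10.1 makes the MRD(-) CR rate primary from Amendment L, on 50 evaluable patients, without an assessment window. The only window in that section, the end of 8 cycles, belongs to the older VGPR objective.

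**The concern.** Footnote m is mainly about imaging and marrow scheduling, but its last clause is a scoring rule: it says how a result will be interpreted. On protein, that rule asks for less than the CR definition. It does not mention immunofixation, does not clearly require both fluids, and does not repeat the confirmation steps.

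The patients it would affect are foreseen. Section 5.1.1 expects some to be MRD negative at the end of cycle 8 without being in CR, and footnote m is the route by which they would become CR later. Serum immunofixation in that phase is done only if clinically indicated, so clearance on electrophoresis may be all that is on record when CR is assigned.

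At stake are the MRD(-) CR rate, its duration, the rate of MRD(-) CR lasting at least a year, and the Fisher comparison of the 18 earlier with the 32 later patients. If two abstractors can score the same patient differently, the reported rate depends on which text they used.

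**Working it through.** **1. The plan's own precision.** The half-width of the 95% interval is 1.96 × √(p(1−p)/n), with n = 50 from Section 10.1.

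- p = 0.70: 1.96 × √(0.21/50) = 0.127, or 12.7 points.
- p = 0.85: 1.96 × √(0.1275/50) = 0.099, or 9.9 points.

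Both match the stated figures.

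**2. The two rules side by side.**

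| Element | Section 6.3 | Footnote m |
|---|---|---|
| Fluids | serum and urine | blood and/or urine |
| Assay | immunofixation | none named |
| Confirmation | two consecutive determinations | silent |
| 24-hour urine | required to document CR | silent |
| Plasmacytomas | must be gone | silent |
| Marrow | ≤5% plasma cells for CR; flow-negative for MRD(-) CR | already negative by immunohistochemistry and flow; no repeat required |

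**3. Who can be scored differently.** Take a flow-negative patient in extension whose protein disappears on electrophoresis and who has no negative immunofixation on record. Section 6.3.2.1 gives nCR, or VGPR if immunofixation is positive. Footnote m, read literally, gives CR and hence MRD(-) CR.

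**4. Direction.** Anyone who meets the full CR definition has cleared protein in both fluids, and so also meets the footnote's protein condition. The converse need not hold. On the protein criteria the footnote can therefore add responders but cannot remove any.

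**5. Gap between marrow and clearance.** If the marrow is from the end of cycle 8, the protein clears at the end of cycle 32, and no later marrow was done, the gap is 32 − 8 = 24 cycles, and 24 × 28 = 672 days. No maximum interval is stated.

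**6. Size.** Let k be the number of patients who are CR only under footnote m. The documents do not give k. Each adds 1/50 = 2.0 points. The table assumes that 35 of 50 (70%) are credited in all.

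| k (assumed) | Rate without them | Shift (points) |
|---|---|---|
| 1 | 34/50 = 68% | 2 |
| 3 | 32/50 = 64% | 6 |
| 5 | 30/50 = 60% | 10 |
| 7 | 28/50 = 56% | 14 |

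The shift exceeds the planned half-width at k = 7 when the rate is 70% (14 > 12.7) and at k = 5 when it is 85% (10 > 9.9). In the cohort comparison, one patient moves the rate by 1/18 = 5.6 points or 1/32 = 3.1 points.

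**The case against.** The strongest reply is that footnote m is a scheduling note whose purpose is to spare a biopsy. The endpoint is defined in Section 6.3.2.1, and nothing says that the footnote overrides it. Most of the stronger readings that a reader might draw fail on the text:

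- **That confirmation is dropped in extension.** Section 6.3.1 applies its two-determination rule to any hematologic response. Its paragraph on urine testing covers cycles 9-32 as well as induction. The footnote is silent on these rules; it does not repeal them.
- **That one fluid is clearly enough.** The and/or may mean whichever fluid carried the protein, and clearance may be meant as negative immunofixation. The footnote says neither.
- **That the bar is lower overall.** A marrow negative by immunohistochemistry and flow is stricter than ≤5% plasma cells. Only the protein evidence and the age of the marrow are in question.
- **That the response is dated too early because the marrow came first.** These patients are already marrow-negative, so the clearance date is already the later of the two. Only the step from clearance to confirmed serologic CR could move it.
- **That the two components never held together.** The documents show only that they need not be observed on the same date. Section 5.1.1 makes later marrows optional, not absent.
- **That the primary rate is shown to be biased.** The footnote acts only from cycle 9. If the primary rate were read at the end of cycle 8, the effect on it would be zero. Section 10.1 reports 17 of the first 18 patients with some form of CR and 16 MRD negative, which does not suggest a large pool of late converters.

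What survives is that the footnote says how the result will be interpreted, which goes beyond waiving a biopsy. That wording conflicts with the CR definition, and no text resolves the conflict.

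**Conclusion.** The concern holds as a conflict between two scoring texts, confined to the protein evidence and to reliance on an earlier marrow. Followed literally, footnote m can credit MRD(-) CR where Section 6.3.2.1 would give nCR or VGPR.

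The effect on the primary rate is conditional. It needs responses after cycle 8 to count, which the plan neither states nor excludes, and it needs at least one patient who is CR only under the footnote. The shift is then 2.0 points per patient, upward on the protein criteria. It may be small, and any particular count is an assumption. The duration, one-year durable rate and cohort comparison are exposed in the same way.

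A reader might infer that the trial runs a separate, easier endpoint in extension and that the reported rate is materially inflated. The documents do not support that: Section 6.3 is not limited to induction, and they give no count of affected patients. The point is worth correcting because it touches the primary endpoint and can be settled by a stated rule.

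**What to change.** 1. State that footnote m waives only the repeat marrow, and that CR in every phase requires the Section 6.3 protein criteria: negative immunofixation in serum and urine, two consecutive determinations, and the 24-hour UPEP.
2. Score all patients by that rule from data already collected. When the negative marrow came first, date MRD(-) CR from the confirmed serologic CR.
3. Flag patients whose only negative marrow predates CR, and patients whose CR lacks the Section 6.3 documentation. Report the MRD(-) CR rate with and without them.
4. State whether responses after cycle 8 count toward the primary rate.

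**Cost.** This takes one footnote edit, a few sentences in Section 10, and an adjudication pass. Footnote g records that all participants had completed cycle 32 by February 2023, and Section 5.1 that biospecimen collection from participants is complete. The change is therefore one of scoring and reporting, with no new biopsy or test. It cannot supply immunofixation or 24-hour urine results that were never obtained, which is why those patients are flagged. The reported rate may be slightly lower.

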## 3.5 COST AND COMPENSATION

#### 3.5.1 Costs

NIH does not bill health insurance companies or participants for any research or related clinical care that participants receive at the NIH Clinical Center. If some tests and procedures performed outside the NIH Clinical Center, participants may have to pay for these costs if they are not covered by insurance company. Medicines that are not part of the study treatment will not be provided or paid for by the NIH Clinical Center.

# 3.5.2 Compensation

Participants will not be compensated on this study.

#### 3.5.3 Reimbursement

The NCI will cover the costs of some expenses associated with protocol participation. Some of these costs may be paid directly by the NIH and some may be reimbursed to the participant/guardian as appropriate. The amount and form of these payments are determined by the NCI Travel and Lodging Reimbursement Policy.

#### 3.6 CRITERIA FOR REMOVAL FROM PROTOCOL THERAPY AND OFF STUDY CRITERIA

Prior to removal from study, effort must be made to have all subjects complete a safety visit approximately 30 days (+/- 7 days) following the last dose of study therapy.

# 3.6.1 Criteria for removal from protocol therapy

- Patients with medically concerning grade 3 or 4 adverse events related to drug therapy may be taken off therapy at the discretion of the principal investigator.
- Patients require more than 2 dose reductions of carfilzomib.
- Toxicity has not resolved after 2 weeks of withholding treatment or up to 3 weeks for infection related treatment
- Grade 3 non-blistering rash or blistering rash of any grade
- Grade 3 neuropathy
- Grade 3 hypersensitivity reaction
- Diagnosis of posterior reversible encephalopathy (PRES) or thrombotic microangiopathy (TMA)
- Patient completes the protocol (as outlined in Section 3.2)
- Progression of disease
- Patient chooses to go off therapy
- The principal investigator may remove patient from protocol therapy if deemed necessary due to medical conditions, compliance, etc.
- Patient becomes pregnant.

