Fall to < 25 x 10  /L	Fall to < 25 x 10  /L Hold both Lenalidomide and Carfilzomib, follow CBC weekl Hold prophylactic anti-coagulation.	
Return to $\geq 25 \times 10^9/L$	Resume lenalidomide at next dose reduction	Resume carfilzomib at full dose*
Subsequent fall to < 25 x 10  /L	Hold both Lenalidomide and Carfilzomib, follow CBC weekly. Hold prophylactic anti-coagulation.	
Return to ≥ 25 x 10  /L	Resume lenalidomide at next dose level reduction  Resume carfilzomib at full dose	

\*Carfilzomib may be dose reduced at the clinical discretion of investigator

Neutropenia (Absolute Neutrophil Count)	Lenalidomide	Carfilzomib
Falls to $< 0.5 \times 10^9/L$ or to $< 1.0 \times 10^9/L$ with fever		filzomib. Add filgrastim if Grade 3 are of 38.3°C or sustained temperature de 4. Follow CBC weekly
Returns to $\geq 1.0 \times 10^9/L$	Resume Lenalidomide at next dose reduction.	Resume Carfilzomib at full dose*
Subsequent drop to $< 0.5 \text{ x}$ $10^9/\text{L}$ or to $< 1.0 \text{ x}$ $10^9/\text{L}$ with fever		
Returns to $\geq 1.0 \times 10^9/L$	Resume Lenalidomide at next dose reduction.	Resume Carfilzomib at full dose*

\*Carfilzomib may be dose reduced at the clinical discretion of investigator.

- 3.3.3 Non-Hematologic Toxicity: Induction Phase
- 3.3.3.1 Toxicity ≥ grade 3 will require appropriate study drug to be held until resolved to ≤ Grade 1 unless specified below. Investigator will determine which drug will be held based on side effect profile and clinical judgment.
- 3.3.3.2 Once toxicity has resolved ≤ grade 1, subsequent doses will be reduced at next dose level (according to table in section 3.3.1) if the adverse event was deemed to be treatment related by the PI. If the adverse event was deemed to be unrelated to treatment, the patient may continue the full dose.
- 3.3.3.3 Readily reversible electrolyte and metabolic abnormalities, infections or diarrhea controlled by appropriate therapy are exempt.
- 3.3.3.4 Patients with Grade 3 or higher peripheral neuropathy, Grade 3 or higher non-blistering rash or blistering rash of any grade, grade 3 or higher hypersensitivity reactions will be removed from protocol therapy.

Lenalidomide Toxicities	Dosing Modifications
Blistering Rash (Any Grade)	Discontinue lenalidomide and remove patient from therapy

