If Posterior Reversible Encephalopathy Syndrome (PRES) is suspected	If PRES is suspected, hold carfilzomib. Consider evaluation with neuroradiological imaging, specifically MRI, for onset of visual or neurological symptoms suggestive of PRES. If PRES is confirmed, permanently discontinue carfilzomib. If the diagnosis of PRES is excluded, carfilzomib administration may resume at same dose, if clinically appropriate.

Version Date: 01/01/2024

Carfilzomib Toxicities	Dosing Modifications
If thrombotic microangiopathy (TTP/HUS) is suspected	Hold carfilzomib and manage per standard of care including plasma exchange as clinically appropriate. If TMA is confirmed and related to carfilzomib, permanently discontinue carfilzomib. If the diagnosis is excluded, carfilzomib can be restarted at the previous dose. If the condition recurs, permanently discontinue carfilzomib.
Hepatic Impairment:	
Mild to moderate liver dysfunction: defined as 2 consecutive values, at least 28 days apart, of: (1) total bilirubin (> 33% direct) > 1x ULN to < 3x ULN OR (2) an elevation of AST and/or ALT with normal bilirubin Grade 3 elevation in ALT and/or AST (> 5x ULN)	25% dose reduction. Dose may be re-escalated if liver function tests return to normal and drug-induced hepatotoxicity is excluded.  Hold carfilzomib until resolution to baseline.  Monitor any abnormality weekly. Resume carfilzomib with a 25% dose reduction if drug-induced hepatotoxicity is excluded.
Grade 3 elevation in total bilirubin	Hold carfilzomib until resolution to baseline. Monitor total bilirubin and direct bilirubin weekly.  Upon resolution of total bilirubin to normal, resume carfilzomib dosing with a 25% dose reduction if druginduced hepatotoxicity is excluded.
Drug-induced hepatotoxicity (attributable to carfilzomib)	Discontinue carfilzomib
Thrombotic Microangiopathy (TMA)	If the diagnosis is suspected, hold carfilzomib and manage per standard of care including plasma exchange as clinically appropriate. If TMA is confirmed, permanently discontinue carfilzomib. If the diagnosis is excluded, carfilzomib can be restarted.

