- 3.3.6.2 Once toxicity has resolved ≤ grade 1 or baseline, subsequent doses will be reduced at next dose level (according to table in Section 3.3.4) if the adverse event was deemed to be treatment related by the PI. If the adverse event was deemed to be unrelated to treatment, the patient may continue the full dose. In the case of renally adjusted doses, dosing modifications are made according to table below.
- 3.3.6.3 Readily reversible electrolyte and metabolic abnormalities or infections controlled by appropriate therapy are exempt.

Version Date: 01/01/2024

Common Lenalidomide Toxicities	Dosing Modifications				
Non-Blistering Rash	
 
If Grade 3, hold lenalidomide dose and restart at next dose reduction once rash improves to ≤ Grade 1
 
If Grade 4, discontinue lenalidomide and remove patient from therapy
 
				
Blistering Rash (Any Grade)	Discontinue lenalidomide and remove patient from therapy				
Venous thrombosis/embolism	Hold lenalidomide and start therapeutic anticoagulation. Restart lenalidomide at investigator's discretion at current dose level.				
Renal Dysfunction: CrCl based on Cockcroft-Gault. (NOTE: Alternatively, MDRD or CKD-epi formulas may be used to estimate eGFR as more accurate indictors of renal dysfunction than CrCl in discrepant cases.)	
 
CrCl 31-50 ml/min – Dose reduce lenalidomide to 10 mg daily from Days 1-21
 
CrCl ≤30 mL/min (not requiring dialysis) – Dose reduce Lenalidomide to 15 mg every 48 hours and see carfilzomib dosing below.
 
CrCl ≤30 mL/min (requiring dialysis) – Decrease Lenalidomide to 5 mg daily and on dialysis days dose lenalidomide after dialysis.
 
				

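### For Grade 3 non-blistering rash in the extended phase, section 3.6.1 and the section 3.3.6 table order incompatible actions, and for confirmed TMA three texts differ, so the safety report must state which rule was applied

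*Combined protocol and SAP*

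**What the plan says.** **Non-blistering rash.** The removal list in section 3.6.1 includes "Grade 3 non-blistering rash or blistering rash of any grade". The list carries no phase restriction, and this entry has no permissive wording. For induction, section 3.3.3.4 likewise removes patients with "Grade 3 or higher non-blistering rash or blistering rash of any grade". For extended dosing, the table in section 3.3.6 has two instructions: "If Grade 3, hold lenalidomide dose and restart at next dose reduction once rash improves to" Grade 1 or less, and "If Grade 4, discontinue lenalidomide and remove patient from therapy".

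**Thrombotic microangiopathy.** The carfilzomib table in section 3.3.3 covers it twice. The row labelled TTP/HUS says "If TMA is confirmed and related to carfilzomib, permanently discontinue carfilzomib". A later row says "If TMA is confirmed, permanently discontinue carfilzomib". Both rows hold carfilzomib on suspicion and allow restart if the diagnosis is excluded. Section 3.6.1 lists as a removal criterion "Diagnosis of posterior reversible encephalopathy (PRES) or thrombotic microangiopathy (TMA".

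**PRES.** The same table says "If PRES is confirmed, permanently discontinue carfilzomib". Section 3.6.1 covers PRES in the entry just quoted.

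No section states an order of precedence between the dose-modification tables and the removal list.

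**The concern.** Restarting a drug at a lower dose and taking the patient off therapy are mutually exclusive. For Grade 3 non-blistering rash from cycle 9 onward, a site that obeys one section breaches the other. Section 8.8 defines a deviation as any non-compliance with the protocol, so either action is open to being logged as one.

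For TMA, what the protocol requires depends on which row is read and whether 3.6.1 is consulted. The texts also leave open whether stopping carfilzomib alone counts as removal from protocol therapy.

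The stake is mainly interpretive. Toxicity is a secondary objective (section 1.1.2), and section 10.2 promises to characterise the safety of the regimen fully. A count of patients taken off therapy for toxicity cannot be interpreted if the same event could properly have led to removal in one patient and a reduced dose in another.

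**Working it through.** The point rests on comparing texts. The only arithmetic is a count of cycles.

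**1. Does 3.6.1 apply in the extended phase?** Yes. It lists completion of the protocol as outlined in section 3.2, and section 3.2 runs to cycle 32. Section 1.2.5 also makes the second year of lenalidomide conditional on no reason for removal being present. It cites section 3.5 for those reasons, but that section now covers cost and compensation; the only such list is 3.6.1.

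**2. Rash, texts side by side.**
- Induction, Grade 3: 3.3.3.4 removes and 3.6.1 removes. They agree.
- Extended phase, Grade 3: the 3.3.6 table holds and restarts one level lower; 3.6.1 removes. They are incompatible.
- Extended phase, Grade 4: the 3.3.6 table removes; 3.6.1 names only Grade 3. No practical conflict arises.

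The rash contradiction is therefore confined to Grade 3 from cycle 9 onward.

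**3. Confirmed TMA, texts side by side** (relevant while carfilzomib is given, cycles 1-8).
- Judged related: both rows stop carfilzomib permanently; 3.6.1 removes from protocol therapy.
- Judged unrelated: the TTP/HUS row does not order a permanent stop. It has already put carfilzomib on hold and permits restart only if the diagnosis is excluded, so the patient stays on hold with no stated next step. The later row stops carfilzomib permanently. Section 3.6.1 removes from protocol therapy.

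**4. Confirmed PRES.** The table stops carfilzomib; 3.6.1 removes from protocol therapy. Removal also stops carfilzomib, so both texts can be satisfied together.

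**5. Is stopping carfilzomib the same as removal?** The documents do not say.
- Section 3.3.1.1 keeps carfilzomib and lenalidomide reductions separate, yet takes the patient off therapy if more than two carfilzomib reductions are needed.
- The tables state removal expressly for blistering rash, but not in the TMA or PRES rows.
- Carfilzomib is also discontinued for drug-induced hepatotoxicity (3.3.3 table) and confirmed PML (section 4.6), and 3.6.1 names neither.

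**6. Size per affected patient.** Extended phase I is cycles 9-20 and the optional phase II is cycles 21-32 (sections 3.2.4 and 3.2.5). For a Grade 3 rash in cycle 9:
- under 3.6.1: 0 further cycles;
- under the 3.3.6 table: up to 20 − 9 = 11 further non-optional cycles, or up to 32 − 9 = 23 if phase II is taken.

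**The case against.** **Treatment is over.** Notes in section 3.4, section 5.1.1 and Appendix C say that all participants had completed cycle 32 by February 6, 2023, and this version is dated 01/01/2024. Rewording will change nobody's treatment. This stands, and it limits the live part of the point to reporting and correction of the record.

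**Investigator discretion and team review resolve it.** The first entry of 3.6.1 lets the principal investigator decide on medically concerning related grade 3 or 4 events, and section 7.4.1 has the team discuss each patient about weekly. This stands only in part. The rash and TMA/PRES entries are separate and not permissive, and the closing discretionary entry allows extra removals without waiving listed ones. Team review may make practice uniform, but it does not show which rule was used.

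**Stronger readings the documents do not support.**
- *PRES is a third contradiction.* It is not: removal satisfies both texts.
- *Carfilzomib may continue in confirmed but unrelated TMA.* It may not on the wording: the TTP/HUS row leaves it on hold. Section 3.3.1.2 and section 3.6.1 also end therapy for toxicity unresolved after two weeks of withholding treatment (up to three for infection-related treatment).
- *Three quarters of planned treatment is affected.* Cycles 9-32 are 24 of 32 cycles (75%), or 24 × 21 = 504 lenalidomide dose-days, but cycles 21-32 are optional. Non-optional extended dosing is 12 of 20 cycles (60%), or 12 × 21 = 252 dose-days. Neither figure measures impact without event counts.
- *PFS, duration of response and durable MRD(-) CR are biased.* Sections 6.3.3, 6.3.4 and 10.2 use removal from therapy neither as an event nor for censoring, and follow-up continues off treatment. Assessment timing could shift, since section 6.3 assesses every third cycle (3 × 28 = 84 days) during extended dosing and every 3-6 months in follow-up. The documents do not allow an effect to be shown.
- *The Grade 3 versus Grade 3 or higher wording is a gap.* Other text already orders removal for Grade 4 rash in both phases. It merits tidying only.

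**Conclusion.** The point holds in a limited form. There is one direct contradiction (Grade 3 non-blistering rash, extended phase) and one set of three differing texts (confirmed TMA, with an unresolved branch when it is judged unrelated). PRES is a difference of scope only.

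Per affected patient, the rash conflict concerns up to 11 non-optional cycles after cycle 9, or up to 23 with the optional year. This assumes the rash falls in cycle 9 and the patient would otherwise have completed treatment; a later rash leaves fewer. The number of affected patients is unknown and may be zero, so no trial-level effect on any endpoint is claimed.

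A stopping rule that cannot be followed as written should still be reconciled and its application disclosed. Nothing here implies which rule is clinically right.

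**What to change.** **Protocol text.** The sponsor should reconcile sections 3.3.3 (including 3.3.3.4), 3.3.6 and 3.6.1:
- state the phase and grade to which the 3.6.1 rash entry applies, so that it agrees with the tables;
- replace the two TMA rows with one that says what follows each outcome, including confirmed but unrelated;
- say whether stopping carfilzomib alone is removal from protocol therapy, which also settles the PRES difference.

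The content of each rule is the sponsor's decision.

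**Safety report (the live part).** Add a listing of every patient with Grade 3 non-blistering rash in the extended phase, confirmed TMA or confirmed PRES, giving cycle, action taken and section applied. Report carfilzomib stopped and all protocol therapy stopped as separate categories. If no patient qualifies, one sentence saying so closes the matter.

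**Cost.** Wording changes in one list, one induction rule and two tables, plus one listing. Section 8.2 already collects adverse-event descriptions and severity. The listing otherwise needs only the treatment action and section applied, taken from existing records where documented; no new patients or assessments are needed.
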